1 STUDY SYNOPSIS

Complete Protocol Title	Continuum™ Metal Bearing System in Total Hip Arthroplasty - A multi-center, prospective, non-controlled post market surveillance study
Protocol Number	09-H03
Short Protocol Title	Continuum™ Metal Bearing System in Total Hip Arthroplasty
Sponsor	Zimmer Biomet GmbH
Manufacturer	Zimmer Biomet GmbH
Study Device(s)	Investigational devices 1. Continuum™ Acetabular Shell 2. Metasul® Taper Liner 3. Metasul Femoral Head Combination device Zimmer® M/L Taper Hip Stem
Study Objectives/Endpoints	The objectives of this study are to obtain survival and outcome data on the Continuum Metal Bearing System when used in primary total hip arthroplasty. This will be done by analysis of standard scoring systems, radiographs and adverse event records. Data will be used to monitor pain, mobility and survivorship, and to confirm the safety and performance of the Continuum Metal Bearing System. Safety will be evaluated by monitoring the frequency and incidence of adverse events. Performance will be determined by comparing the overall pain and functional performances, survivorship, subject quality-of-life and radiographic parameters of study subjects who received the Continuum Metal Bearing System. Pain and functional performance will be measured using the Harris Hip Score, survivorship will be based on removal or intended removal of the device, subject quality-of-life will be determined by evaluation of the SF-12, and radiographic parameters by analysis of x-rays. In addition, metal ion levels (cobalt, chromium and titanium) and renal function (BUN, Creatinine and GFR) will also be analyzed preoperatively and again at 6 months, 1, 2 and 5 years.
Indications/Target Population	Patients, suffering from severe hip pain and disability requiring total hip arthroplasty.
Inclusion/Exclusion Criteria	Inclusion Criteria 
• Patient is 18 to 75 years of age, inclusive.• Patient is skeletally mature.

	
• Patient qualifies for primary unilateral or bilateral total hip arthroplasty (THA) based on physical exam and medical history including the following:
◦ Avascular necrosis (AVN)◦ Osteoarthritis (OA)◦ Inflammatory arthritis (i.e. Rheumatoid arthritis)◦ Post-traumatic arthritis• Patient has no history of previous prosthetic replacement device (any type, including surface replacement arthroplasty, endoprostheses, etc.) of the affected hip joint(s).• Patient has a Harris Hip Score <70 in the affected hip• Patient is willing and able to provide written informed consent.• Patient is willing and able to cooperate in the required post-operative therapy.• Patient is willing and able to complete scheduled follow-up evaluations as described in the Informed Consent.• Patient has participated in the Informed Consent process and has signed the Ethics Committee approved informed consent.
--	--

Exclusion Criteria

- The patient is:
 - A prisoner
 - Mentally incompetent or unable to understand what participation in the study details.
 - A known alcohol or drug abuser
 - Anticipated to be non-compliant.
- The patient has a neuromuscular disorder, vascular disorder or other conditions that could contribute to prosthesis instability, prosthesis fixation failure, or complications in postoperative care.
- The patient has a neurologic condition in the ipsilateral or contralateral limb which affects lower limb function.
- The patient has a diagnosed systemic disease that could affect his/her safety or the study outcome.
- The patient is known to be pregnant.
- The patient is unwilling or unable to give consent, or to comply with the follow-up program.
- The patient has received an investigational drug or device within the previous 6 months.
- The patient has an active or latent infection in or about the affected hip joint or an infection distant from the hip joint that may spread to the hip

	
hematogenously.
 
• The patient has insufficient bone stock to fix the component. Insufficient bone stock exists in the presence of metabolic bone disease (i.e. osteoporosis), cancer, and radiation. Note: Dual Energy X-ray Absorptiometry (DEXA) may be used to assess the presence of adequate bone stock.• The patient has known local bone tumors and/or cysts in the operative hip.• The patient has a known allergic reaction to one or more of the implanted material.• The patient is Grade III obese with a Body Mass Index (BMI) ≥ 40.• The patient has osteoradionecrosis in the affected hip joint• Kidney insufficiency (Kidney insufficiency will be determined based on eGFR value.)
Study Design	Multi-center, prospective, non-controlled.
Clinical Phase	Post-market
Sample Size	A total of 100 patients will be enrolled into the study.
Length of Study	11 years (1 years of enrollment (all sites) and 10 years of follow-up)
Materials and Methods	Case report forms will be completed at Pre-op, Surgery, Immediate Post-op, and the 6 weeks, 6 months, 1, 2, 3, 5, 7 and 10 years intervals.
Data Collection	Electronic
Statistical Reporting	Data collected will be summarized and reported to each participating investigator. Statistical analysis will be conducted by Zimmer Biomet or its designee. Survivorship will be evaluated using Kaplan-Meier.
Scores/Performance Assessments	Evaluations will be made using the Harris Hip Score (HHS), SF-12, EuroQol (EQ-5D) and Oxford Hip Score (optional).
Standards	The PMCF is compliant with the below: 
• ISO 14155 Standard for the Clinical Investigation of Medical Devices (part 1 and 2)• The Declaration of Helsinki (DoH) - Ethical principles for medical research involving human subjects.
Study Funding	Funding for this clinical study is made available by Zimmer Biomet to support clinical data collection, IRB/EC review fees and other expenses associated with the conduct and execution of this study protocol as outlined in the fully executed Clinical Trial Agreement. .

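### Does a non-controlled, descriptive study that promises to confirm safety and performance need its aim reworded and its survival limits prespecified?

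*Combined protocol and SAP*

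**What the plan says.** The Study Objectives/Endpoints entry of the synopsis begins "The objectives of this study are to obtain survival and outcome data". It then says that the data will serve to monitor pain, mobility and survivorship and "to confirm the safety and performance of the Continuum Metal Bearing System". Two sentences give this content: "Safety will be evaluated by monitoring the frequency and incidence of adverse events" and "Performance will be determined by comparing the overall pain and functional performances, survivorship, subject quality-of-life and radiographic parameters of study subjects". The survival event is defined: "survivorship will be based on removal or intended removal of the device".

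The Study Design entry reads "Multi-center, prospective, non-controlled" and the Sample Size entry "A total of 100 patients will be enrolled into the study", with no justification of that number. Follow-up is 10 years, with visits at 1, 2, 3, 5, 7 and 10 years after the early ones. The inclusion criteria admit one-sided and two-sided primary replacement.

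The Statistical Method section of the SAP makes all summaries descriptive. It attaches 95% limits to changes over time in categorical data and to contrasts in continuous data. Implant survival gets Kaplan-Meier estimates with crude rates beside them, and complications get counts and percentages. Neither of those two sentences mentions an interval, and no unit of analysis is named for survival.

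**The concern.** To confirm something, one needs a standard to confirm it against. Here every subject receives the same system, no external benchmark is cited, and survivorship, unlike a hip score, has no preoperative value to compare with. The word therefore seems to promise more than the design can give.

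The SAP sentence on survival sharpens the worry. The plan asks for 95% limits elsewhere, so their absence from the outcome followed for 10 years could be read as deliberate. A bare survival percentage from 100 patients, some of them lost over a decade, would not show how much lower the true figure might be, and a reader might take it as the promised confirmation. Two smaller points add to this. The crude rate ignores censoring and so flatters the device when patients are lost. If hips are counted as independent, bilateral patients make the limits slightly too narrow.

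**Working it through.** **The plan's own figure.** The sample size of 100 cannot be re-derived. The documents give no target precision, reference survival, error rate, power or expected loss. That fits a descriptive study and contradicts nothing.

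**What depends on *confirm*.** The SAP contains no hypothesis, margin, threshold or decision rule. Removing the word would leave every planned table unchanged. *Comparing* has a natural meaning for pain, function and quality of life: change over the scheduled visits, which is what the SAP's 95% limits address. Only for survivorship does it lack a counterpart.

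**What a real confirmation would need (illustration).** Assume a 90% reference and a one-sided 2.5% exact binomial test with n = 100. At least 96 survivors are then required (actual error 0.0237). Power is 44% if true survival is 95% and 82% if it is 97%. The plan proposes no such test.

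**Width of the unmentioned limits.** From the documents: n = 100, 10 years. Assumed: survival S of 0.95 or 0.90 at 10 years, constant failure hazard λ = −ln(S)/10, and independent loss L with hazard μ = −ln(1−L)/10.

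- Var(ln S) = [λ/(λ+μ)] × [exp(10(λ+μ)) − 1] / n. With no loss this is (1−S)/(nS).
- Standard error on the log-log scale: se = √Var / (−ln S).
- With k = exp(1.96 se), the limits are S^k and S^(1/k).

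Example, S = 0.95 with no loss: Var = 0.05/95 = 0.00053, se = 0.447, k = 2.40, limits 88.4% to 97.9%.

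| Survival | Loss | At risk at 10 years | 95% limits | Width (points) |
|---|---|---|---|---|
| 95% | 0% | 95 | 88.4–97.9% | 9.5 |
| 95% | 40% | 57 | 87.0–98.1% | 11.1 |
| 90% | 0% | 90 | 82.2–94.5% | 12.3 |
| 90% | 40% | 54 | 80.7–95.0% | 14.3 |

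**Crude rate.** Expected crude failure = [λ/(λ+μ)] × [1 − exp(−10(λ+μ))]. With 40% loss this is 3.92% against a true 5%, and 7.87% against a true 10%. The understatement is 1.1 and 2.1 points. With 20% loss it is 0.5 and 1.0 points. The Kaplan-Meier estimate is the main one and does not carry this bias when loss is independent of failure.

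**Hips or patients.** With b bilateral patients and within-patient correlation ρ, the variance inflation is 1 + 2bρ/(100 + b). For an assumed b = 20 and ρ = 0.5 it is 1 + 20/120 = 1.17. The lower limit moves from 89.2% to 88.5% at 95% survival, and from 83.1% to 82.4% at 90%. In simulation without loss (ρ = 0.5), coverage of unadjusted 95% limits was about 92% in the least favourable case (30 bilateral patients, 90% survival). It was about 93.5% to 95.4% in the other three combinations of 20 or 30 bilateral patients with 90% or 95% survival.

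**The case for a change.** The best case for a change is that it costs almost nothing. The SAP has a separate sentence for survival with its own companion statistic, and limits are not in it. The general sentence on 95% limits concerns differences over time, so it does not clearly reach a survival estimate. If software prints the limits anyway, writing them down is free, and leaving them out permits a 10-year device report without them. At an estimated 95% the lower limit would be near 87% to 88%, which a reader ought to know.

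The textual reading stands: the documents state no interval, number at risk or unit for survival. The width also stands under the assumptions shown. What does not follow is that the plan is defective. The SAP lists routine summaries and not a closed set of table shells, and nothing in it prevents limits from being reported. Because they derive from data already collected, they can be added at any report without affecting design, conduct or validity. The fear that a reader will mistake a point estimate for a formal confirmation is speculative, since the title, the Study Design entry and the SAP all present a non-controlled, descriptive study.

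The rewording would carry a small cost of its own. Dropping *comparing* altogether would take out comparisons over time that the SAP does plan for the Harris Hip Score and SF-12. Requiring a cluster-robust variance is not supported either: the documents give no bilateral count or correlation, and in the simulations at 95% survival the robust limits over-covered at about 97%.

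**Conclusion.** No change is called for. *Confirm* is loose wording in a sentence that also says the data will be used to monitor, under an objective already phrased as obtaining data, and no analysis or decision turns on it. The missing interval, number at risk and unit are reporting details that a competent analyst fills in when producing a Kaplan-Meier table, keeping one unit throughout. Their absence makes no planned estimate wrong.

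The limits would be about 9.5 to 14.3 points wide at 10 years, the crude rate would understate failure by 0.5 to 2.1 points, and ignoring bilateral pairing would shift the lower limit by about 0.7 points. All of these rest on assumptions that the documents neither give nor exclude: 90% or 95% survival, constant hazards, loss independent of failure (0% to 40% for the widths, 20% to 40% for the crude rate) and, for the last figure, 20 bilateral patients with correlation 0.5. The conclusion would differ if the study were later used to claim success against a benchmark. That would need a reference value and a rule fixed beforehand, and the present plan makes no such claim.

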2 STATISTICAL ANALYSIS PLAN

Statistical Method

Data collected in the study will be summarized descriptively. Descriptive summaries will be used for the basis of all study reports, including a summary of the clinical performance of the Continuum Metal Bearing System in primary total hip arthroplasty, and may be used for reports and to support presentations and publications as needed.

Summaries will routinely describe categorical data as counts and percentages, and ninety-five percent confidence limits will be generally used to assess differences over time. Routine summaries describing continuous data will be in the form of means, medians, standard deviations, minima, and maxima, and ninety-five percent confidence intervals will be used to contrast differences.

Routine summaries of implant survival will be described using the Kaplan-Meier method and these will be accompanied with the corresponding crude rates (expressed as percentages). Routine summaries of complication data will be in the form of frequencies and percentages. Summaries may be further generated for strata within the study population, (e.g., males and females, at different cut-points in the body mass index continuum, etc.).

Patient confidentiality will be protected at all times, and patient identifiers will not be included in study summaries.

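### The planned Kaplan-Meier and undefined crude rates do not estimate the actual 10-year risk of device removal once both deaths and losses occur; a cumulative incidence should be added

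*Combined protocol and SAP*

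**What the plan says.** The Statistical Method text of the SAP (section 2) gives the whole survivorship analysis in one sentence: "Routine summaries of implant survival will be described using the Kaplan-Meier method and these will be accompanied with the corresponding crude rates", with the crude rates shown as percentages. The synopsis (section 1, Statistical Reporting) adds only that "Survivorship will be evaluated using Kaplan-Meier".

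The event is set in the synopsis under Study Objectives/Endpoints: "survivorship will be based on removal or intended removal of the device". Death is not part of it.

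Three design features bear on the point:
- Age at entry: "Patient is 18 to 75 years of age, inclusive".
- Duration: "11 years (1 years of enrollment (all sites) and 10 years of follow-up".
- Size: "A total of 100 patients will be enrolled into the study".

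The analysis is descriptive throughout: "Data collected in the study will be summarized descriptively". For categorical data the SAP says that "ninety-five percent confidence limits will be generally used to assess differences over time", and it plans similar intervals for continuous data. It does not explicitly attach an interval to the implant-survival estimate.

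The documents do not mention death, give a censoring rule for death or loss to follow-up, define the denominator of the crude rate, or plan a cumulative-incidence estimate.

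**The concern.** A patient who dies with the implant in place can no longer have it removed. Someone aged 75 at entry would be 85 at the last visit, so some deaths before year 10 are to be expected. With death outside the event, standard Kaplan-Meier practice censors it. The curve then describes how long devices would last if nobody died, and 1-KM cannot fall below the proportion of patients who actually have the device removed.

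The companion figure has a different weakness. If the crude rate is removals divided by all implanted patients, anyone lost early counts as event-free, and removals after the loss are missed.

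Survivorship is a stated objective, and descriptive estimates are all that the study will produce. A report could therefore carry two different 10-year failure figures, with nothing in the SAP to say what each one estimates or why they differ.

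**Working it through.** The plan has no figure of its own to reproduce: it states no removal rate, mortality, expected loss, target survival or power calculation. The check compares the two planned figures with the cumulative incidence of removal.

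**Inputs from the documents:** 10-year horizon; 100 patients, taken as one hip each although bilateral procedures are allowed.

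**Assumed inputs:** net 10-year removal risk 10% (range 5-20%), 10-year mortality 5-30%, 10-year loss to follow-up 0-30%. Each is the risk that would apply if the other causes of leaving the study were absent. Deaths and losses are taken as independent of removal, and hazards as constant.

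**Formulas**
- hr = -ln(1 - removal)/10, hd = -ln(1 - mortality)/10, hl = -ln(1 - loss)/10
- 1-KM with death censored = the net removal risk
- Cumulative incidence = hr/(hr+hd) × [1 - exp(-10(hr+hd))]
- Crude rate over all implanted = hr/(hr+hd+hl) × [1 - exp(-10(hr+hd+hl))]

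**Worked case (removal 10%, mortality 20%, loss 20%)**
- hr = 0.010536, hd = hl = 0.022314
- 1-KM = 10.0%
- Cumulative incidence = 0.010536/0.032850 × (1 - 0.9 × 0.8) = 0.3207 × 0.28 = 8.98%
- Crude = 0.010536/0.055165 × (1 - 0.9 × 0.8 × 0.8) = 0.1910 × 0.424 = 8.10%

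**Effect of mortality on 1-KM (removal 10%)**

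| Mortality | 1-KM | Cumulative incidence | Excess (points) | Ratio |
|---|---|---|---|---|
| 5% | 10.00% | 9.75% | 0.25 | 1.025 |
| 10% | 10.00% | 9.50% | 0.50 | 1.053 |
| 20% | 10.00% | 8.98% | 1.02 | 1.114 |
| 30% | 10.00% | 8.44% | 1.56 | 1.185 |

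**Effect of loss on the crude rate (removal 10%, mortality 20%; cumulative incidence 8.98%)**

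| Loss | Crude | Relative shortfall |
|---|---|---|
| 0% | 8.98% | none |
| 10% | 8.55% | 1 - 8.55/8.98 = 5% |
| 20% | 8.10% | 1 - 8.10/8.98 = 10% |
| 30% | 7.63% | 1 - 7.63/8.98 = 15% |

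**Sampling error.** The large-sample Greenwood variance is (1 - removal)² × (hr/100) × [exp(10h) - 1]/h, with h = hr+hd+hl. In the worked case this is 0.81 × 0.00010536 × 0.7361/0.055165 = 0.00114. The standard error is 3.37 points and the 95% half-width 6.61 points. Over all combinations at 10% removal risk, the half-width runs from 5.96 to 7.12 points.

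**Sensitivity.** At 5% net removal risk the excess of 1-KM is 0.12-0.79 points, and at 20% it is 0.49-3.07 points. Timing matters too. At 10% removal and 20% mortality with a constant death hazard, early removals (Weibull shape 0.5) give an excess of 0.68 points and late removals (shape 2) give 1.36. The largest excess found, with late removals and 30% mortality, is 2.07 points at 10% removal risk and 4.09 points at 20%, a ratio of about 1.26 in both.

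**The case against.** The strongest reply is that the plan asks about the device. Kaplan-Meier with death censored estimates net implant survival, a recognised quantity that suits a device-survivorship objective if censoring is independent, and the documents nowhere name the absolute risk to a patient as the target. This stands, and it is why Kaplan-Meier should stay.

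A reader might infer that the study is left without any valid estimate of removal risk. The documents do not support that. Kaplan-Meier is valid for the net quantity, and with complete follow-up the crude percentage equals the cumulative incidence exactly (8.98% in both at 10% removal and 20% mortality). Under the assumptions used here, the two planned figures also bracket the cumulative incidence. Nor do the documents say that death is censored or that the crude rate is taken over all implanted patients. Both are inferences, the first from the event definition and usual practice.

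The size is also fairly challenged. Every rate is assumed. Age 75 is a ceiling in a range that starts at 18, no age distribution is given, and the exclusions for systemic disease, vascular disorders and kidney insufficiency may keep mortality low. The study tests no hypothesis, so no planned decision turns on about one point.

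What remains is that the differences are systematic: a wide interval around one quantity does not turn it into an estimate of another. A reader given 10.0% and 8.1% has no planned figure for the value between them.

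**Conclusion.** The point holds as a modest, inexpensive improvement to the reporting. When both deaths and losses occur, no planned figure estimates the proportion who actually have the device removed, assuming that death is censored and the crude denominator is all implanted patients.

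At an assumed 10% net removal risk with constant hazards, 1-KM exceeds that proportion by about 0.3 points at 5% mortality and 1.6 points at 30% (3-19% relative), and the crude rate falls about 5-15% short at 10-30% loss. The direction of both errors is secure under independent censoring. Their size depends on rates and timing that the documents do not give. In the scenarios examined, both differences are smaller than the sampling error with 100 patients, so they would not by themselves overturn a conclusion about the device.

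**What to change.** In the Statistical Method text of the SAP:
- Keep Kaplan-Meier, labelled as net implant survival with death censored, and state how loss to follow-up is handled.
- Add the Aalen-Johansen cumulative incidence of removal or intended removal, with death as a competing event and a 95% CI, at 1, 2, 3, 5, 7 and 10 years.
- Report numbers at risk, deaths and losses at each of these times.
- If the crude rate is kept, state its denominator. There is no need to delete it.

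The cost is a short addition to the SAP, one extra routine estimate and a line in each report on why the figures differ. The estimate needs dates of removal, death and last contact, which a removal-survivorship analysis needs anyway. Like Kaplan-Meier, it assumes that losses are unrelated to the risk of removal, so it does not remove the need to report them.

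### Complications that do not lead to implant removal have no summary that allows for incomplete follow-up over 10 years; a cumulative incidence estimate beside the percentages is a cheap improvement.

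*Combined protocol and SAP*

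**What the plan says.** The SAP's Statistical Method section treats two outcomes differently in consecutive sentences. On implants: "Routine summaries of implant survival will be described using the Kaplan-Meier method", accompanied by crude rates. On complications: "Routine summaries of complication data will be in the form of frequencies and percentages". For categorical data in general it adds 95% confidence limits to assess change over time. The only further summaries it names are by strata such as sex or body mass index.

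The synopsis fixes the scope of the survival analysis: "survivorship will be based on removal or intended removal of the device". On safety it says: "Safety will be evaluated by monitoring the frequency and incidence of adverse events". Neither document defines that incidence, its estimator or its denominator.

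On size and duration the synopsis says: "A total of 100 patients will be enrolled into the study". It plans one year of enrolment and ten years of follow-up, with visits at 3, 5, 7 and 10 years in the later part. Bilateral cases are eligible. The upper age limit is 75: "Patient is 18 to 75 years of age, inclusive". No loss allowance and no missing-data rule is given.

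**The concern.** A percentage of all implanted patients treats someone who left follow-up at year 3 as if complication-free to year 10. Kaplan-Meier avoids this, but here its event is removal or intended removal. Complications leading to removal are therefore partly covered by the survival analysis, and the others are not.

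Safety is a stated purpose of the study, and the SAP makes the descriptive summaries the basis of all study reports. For long-term complications without removal, readers would have a percentage that falls as loss rises, and nothing beside it from which a 10-year risk could be read.

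**Working it through.** **No plan figure to reproduce.** The sample size of 100 is stated without derivation, and the documents give no loss, complication rate, timing or death rate. From the documents come only N = 100 and 10 years. Everything else below is assumed and shown as a range.

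**1. Expected percentage of all implanted patients.** Let F be the true 10-year risk and L the proportion lost by year 10, with loss exponential and unrelated to complications. At constant hazard, h = -ln(1-F)/10 and c = -ln(1-L)/10, and the expected percentage is h/(h+c) × [1 - exp(-10(h+c))].

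Example with F = 0.10 and L = 0.30: h = 0.010536, c = 0.035667, h/(h+c) = 0.228 and exp(-10(h+c)) = 0.9 × 0.7 = 0.63. The result is 0.228 × 0.37 = 0.0844, or 8.4%.

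For other timings, the percentage is the integral over 0 to 10 years of the event density times the probability of still being in follow-up.

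| True risk and timing | 10% lost | 20% lost | 30% lost | 50% lost |
|---|---|---|---|---|
| 10%, constant hazard | 9.5 | 9.0 | 8.4 | 7.3 |
| 10%, rising hazard (Weibull shape 2) | 9.3 | 8.6 | 7.9 | 6.4 |
| 10%, events in years 5-10 only | 9.2 | 8.5 | 7.7 | 6.0 |
| 10%, events within 90 days | 9.99 | 9.97 | 9.96 | 9.92 |
| 30%, constant hazard | 28.6 | 27.1 | 25.5 | 22.1 |

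With no loss, every row equals the true risk.

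**2. Against sampling error.** The 95% half-width is 1.96 × sqrt(F(1-F)/100): 5.9 points at 10% risk and 9.0 at 30%. At constant hazard and 10-30% loss, the bias is 0.5 to 1.6 points at 10% risk and 1.4 to 4.5 points at 30% risk. Both are below the half-width.

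**3. Accuracy.** These figures are from a simulation of 20,000 trials of 100 patients, at constant hazard and without deaths. Coverage is that of the true risk by a 95% Wilson interval on the percentage. Root-mean-square error is given as percentage v time-to-event estimate, in points.

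| | 10% lost | 20% lost | 30% lost | 50% lost |
|---|---|---|---|---|
| Coverage, 10% risk | 94 | 93 | 92 | 86 |
| Coverage, 30% risk | 93 | 89 | 82 | 55 |
| Error, 10% risk | 3.0 v 3.1 | 3.1 v 3.2 | 3.2 v 3.3 | 3.8 v 3.6 |
| Error, 30% risk | 4.7 v 4.7 | 5.4 v 4.9 | 6.3 v 5.1 | 8.9 v 5.6 |

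The time-to-event interval covers 95-96% throughout.

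**4. Why death should compete.** Let the death hazard be b = -ln(1-D)/10, and solve a/(a+b) × [1 - exp(-10(a+b))] = F for the complication hazard a. One minus Kaplan-Meier with deaths censored then tends to 1 - exp(-10a). For a true 10% this is 10.5% with D = 10% and 11.1% with D = 20%. For a true 30% it is 31.5% and 33.2%. In simulation with 10% deaths and 10-50% loss, Aalen-Johansen averaged 9.9-10.0% and 29.8-30.2%.

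**5. Numbers at risk at year 10.** With 10% complication risk and 10% deaths, exp(-10a) = 1 - 0.105 = 0.895. With 20% loss, 100 × 0.895 × 0.90 × 0.80 = 64 patients remain event-free and in follow-up. With 50% loss, 100 × 0.895 × 0.90 × 0.50 = 40.

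**The case against.** The strongest reply is that nothing is wrong here. The study is non-controlled and descriptive, a percentage correctly describes what was observed, the plan promises no 10-year complication risk, and no decision depends on one. All of that stands, and it is why this is an improvement and not an error.

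The gain also depends on the inputs. At 10% risk and 10-30% loss, the percentage has slightly smaller root-mean-square error than the time-to-event estimate, and its interval still covers 92-94%. The coverage of 55% needs both 30% risk and 50% loss. This stands too, and is a reason to add to the percentages and not replace them. What remains is that a confidence interval shows sampling error but not this bias, which runs in the reassuring direction and grows with loss and late onset.

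The direction of bias is not fixed by the plan, since no denominator is defined. Percentages of patients seen at each visit would behave differently. So would loss related to complications.

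Finally, the SAP speaks of routine summaries, which does not forbid others, and the synopsis mentions incidence. A reader might infer that the plan rules out a time-to-event analysis of complications. The text does not say so; it simply plans none.

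**Conclusion.** The gap is real but modest. Complications leading to neither removal nor intended removal have no planned summary that allows for incomplete follow-up. The understatement in the percentage is conditional on an all-implanted denominator, non-trivial loss unrelated to complications, and events that are not early. At a true risk of 10% and constant hazard it runs from 0.5 points with 10% loss to 2.7 points with 50% loss. With events confined to years 5-10 it reaches 4.0 points at 50% loss. All loss, risk, timing and death figures are assumptions.

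Two stronger readings should be resisted. A reader might infer that the study will misreport its safety results; the documents do not support this, because actual loss is unknown and the percentage is a valid count of what was seen. A reader might also infer that no complication is handled with censoring in mind; those that end in removal or intended removal enter the Kaplan-Meier analysis through that event.

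**What to change.** Keep the counts and percentages, and state the denominator and the unit (patient or hip). Then add to the SAP:

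> *For the main complication types, and for first device-related complication not leading to removal or intended removal, cumulative incidence will be estimated at 1, 2, 5 and 10 years with 95% CI and number at risk (Aalen-Johansen). Event-free patients are censored at last contact; death and, for the non-removal estimate, implant removal are competing events.*

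The estimates by type and without removal are the substance of the change. A pooled first-complication estimate could be dominated by early events, where there is almost no bias to correct, and would hide later complications in the same patient.

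The cost is these two sentences and a few tables, with no change to sample size or visits. There are four downsides:

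- Complication onset dates must be confirmed as recorded, because the documents do not describe the adverse-event fields.
- In later follow-up, a complication found only at a visit has its onset known only to within 2-3 years. The calculations above assume exact dates.
- Variance is slightly higher when events are rare: the standard deviation is 3.2 v 2.9 points at 10% risk and 20% loss.
- Late estimates rest on fewer patients (about 64 or 40 of 100 at year 10 in the cases worked above), and they still assume that loss is unrelated to complications.
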